6.5. Updosing and Dose Modifications of Study Drug

6.5.1. Updosing and Downdosing of Study Drug

Initial updosing to a new level will be attempted sequentially every 2 weeks per the updosing regimens in Table 3. A telephone call follow-up will be done 1 day after each updosing visit to inquire about allergic symptoms and promote adherence to treatment, and remind subjects to complete the daily diary. As shown in Table 5, subjects who fail to tolerate dose levels of at least 50 mg/day will discontinue study drug; these subjects will remain in the study per Section 7.2.

Subjects who tolerate at least 50 mg/day will continue in the updosing portion of the study, and will return to the clinic every 2 weeks for updosing under direct medical supervision until the randomized target dose of 1500 mg/day (100 mg per food source; low-dose regimen) or 4500 mg/day (300 mg per food source; high-dose regimen) is achieved (Figure 1). If a subject fails 3 updosing attempts to any dose level above 50 mg/day, the site should contact the Study Medical Monitor for further guidance regarding additional updosing. Subjects who are unable to reach the randomized target dose will continue on the highest dose level they are able to reach, as long as the dose of study drug is at least 50 mg.

Subjects who do not tolerate the current dose level may be permitted to downdose to a previous dose level at the discretion of the investigator.

Subjects must not be updosed for 3 days after the cessation of administration of corticosteroids.

For guidance regarding updosing during a public health emergency, refer to Appendix 6 (Section 10.6).

Table 5: Updosing Decisions for Study Drug

Dose Level Attempted during Updosing Phase (mg)	Tolerated Dose within 3 Attempts?	Instructions
5	Yes	Continue to the next dose level.
	No	Discontinue study drug and remain in the study per Section 7.2. An additional subject will be randomized without impacting the overall 2:2:1:1 randomization ratio.
20	Yes	Continue to the next dose level.
	No	Discontinue study drug and remain in the study per Section 7.2.
50	Yes	Continue to the next dose level; subject is eligible to continue the study.
	No	Discontinue study drug and remain in the study per Section 7.2.
Any dose above	Yes	Continue to the next dose level.
50 mg	No	Contact Study Medical Monitor for further instructions.

In-Clinic Observation after Initial Study Drug Administration and Every Updosing

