7.2. Discontinuation of Study Drug

It may be necessary for a subject to permanently discontinue study drug prior to planned completion of the treatment regimen per predefined stopping rules (see Section 7.1 above), or a subject may discontinue study drug for reasons including, but not limited to, the following:

- Adverse event
- Lost to follow-up
- Noncompliance with study drug
- Investigator decision
- Pregnancy
- Protocol deviation
- Termination of study by Sponsor
- Withdrawal by subject/legally authorized representative

The reason for subject discontinuation from study drug will be recorded in the source documentation and on the appropriate eCRF.

Permanent discontinuation of study drug does not mean withdrawal from the study, and the subject will be encouraged to remain in the study and continue to complete all study visits as per the SoA (Section 1.3); for these subjects, the Exit DBPCFC at Week 40 will be optional and at the discretion of the subject and investigator. The investigator is encouraged to consult with the Study Medical Monitor (or designee) prior to determining whether a subject should take part in the Exit DBPCFC in this situation.

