10.4.2.4. Study Participation following Completion of Eosinophilic Esophagitis Evaluation

If a subject discontinues study drug, the subject will be encouraged to continue remaining study assessments without treatment (and without Exit DBPCFC). If the subject chooses not to complete all study visits as per the SoA, the site will follow up with the subject every 2 weeks regarding status of his or her EoE-associated symptoms through the duration of the study or until suspected EoE-related symptoms have resolved (whichever is earlier).

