In addition to the analyses described above, the following supportive analyses will be performed using the primary endpoint:

- The Farrington-Manning non-inferiority test will be used to compare the primary endpoint response rates of high-dose ADP101 vs. pooled placebo and low-dose ADP101 vs. pooled placebo using a margin of inferiority of 15%.
- The comparison of the primary endpoint between the pooled ADP101 vs. pooled ADP101 will be provided using the Fisher's exact test.
- The analysis of the primary endpoint will be performed for 2 additional populations, 1) all subjects (pediatric and adult subjects combined) and 2) adult subjects in the ITT Population. The same method as described in the primary analysis above (for pediatric subjects) will be used for all subjects and the unadjusted p-values will be reported. Descriptive statistics corresponding to the primary endpoint response rates will be reported for adult subjects.

The plots of subjects with a ≥ 600 mg desensitization response will be provided for pediatric, adult and all subjects in the ITT population and pediatric subjects in the PP population.

Subgroup Analysis

Subgroups of ITT subjects who reached their target dose as their maintenance dose (see Section 6.7) will be analyzed for the primary endpoint. The subjects with ≥ 600 mg desensitization response by reached target dose will be plotted for pediatric subjects in the ITT population.

The 15 ADP101 individual foods will be consolidated into 9 foods/food groups, including peanut, tree nuts (almond, cashew, hazelnut, pecan, pistachio, or walnut), milk, egg, soy, wheat, shrimp, finfish (codfish or salmon), and sesame. Descriptive statistics, such as response rate differences and corresponding 95% CIs, will be provided for each ADP-101 food/food group above as long as there is sufficient sample size in that food/food group. The response rate for each food/food group will be based on the number of subjects with qualifying food allergies within the category.

Supplemental Analyses using the Estimand Framework

The primary and top secondary endpoint will be analyzed using the Estimand framework outlined in the E9(R1) (Statistical Principles for Clinical Trials: Addendum: Estimands and Sensitivity Analysis in Clinical Trials) guidance. The intercurrent event of interest is study discontinuation without completing the exit DBPCFC for any of the subject's qualifying food allergies.

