| Intercurrent event = Study discontinuation prior to week 40 Exit DBPCFC | Strategy for Addressing the Intercurrent Event Type and its Description |
|--|---|
| Type A: Study discontinuation due to AE | Treatment Policy Strategy: impute using J2R (jump to reference) by setting to non-responder to each qualifying food |
| Type B: Study discontinuation due to administrative reasons including COVID-related site closure, summer camp attendance or academic reasons | Treatment Policy Strategy: impute using J2R by setting to non-responder to each qualifying food Hypothetical Strategy: impute using subject's respective treatment group's response rate |
| Type C: Study discontinuation due to fatigue, taste, texture or volume of IP | Treatment Policy Strategy: impute using J2R by setting to non-responder to each qualifying food Hypothetical Strategy: impute using subject's respective treatment group's response rate |

The analyses will be done where (i) each type of study discontinuation will be analyzed using the Treatment Policy Strategy, (ii) each type of study discontinuation will be analyzed using the Hypothetical Strategy and (iii) a Hybrid Strategy where Type A and C will be analyzed using

Treatment Policy and Type B will be analyzed using Hypothetical Strategy, as well as (iv) a Hybrid Strategy where Type A will be analyzed using Treatment Policy and Type B will be analyzed using Hypothetical Strategy.

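### The supplemental estimand analyses take leaving the study, not stopping study drug, as the intercurrent event, so the hypothetical strategy values two same-reason drug stoppers differently according to whether they stay on study

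*SAP*

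**What the plan says.** The estimand text in SAP 7.8.1 says: "The intercurrent event of interest is study discontinuation without completing the exit DBPCFC". The table beneath it is headed "Intercurrent event = Study discontinuation prior to week 40 Exit DBPCFC", and each of its three rows (A: adverse event; B: administrative; C: fatigue, taste, texture or volume of product) is a kind of study discontinuation. Under the treatment policy strategy the rule for Types B and C is "impute using J2R by setting to non-responder to each qualifying food", and Type A has the same rule. The hypothetical strategy imputes the subject's own group's response rate.

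Four analyses follow. Analysis (i) uses treatment policy throughout. In (ii), "each type of study discontinuation will be analyzed using the Hypothetical Strategy". In hybrids (iii) and (iv), "Type B will be analyzed using Hypothetical Strategy"; Type A is treatment policy in both, Type C is treatment policy in (iii), and (iv) does not mention Type C.

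The protocol treats stopping drug and leaving the study as separate events:
- Section 7.2: "Permanent discontinuation of study drug does not mean withdrawal from the study". These subjects are encouraged to stay, and their Exit challenge is optional.
- Table 5 (Section 6.5.1), for failure at the 5, 20 or 50 mg step: "Discontinue study drug and remain in the study per Section 7.2". Section 8.1.1.1 plans Exit challenges for subjects who reach at least 50 mg.
- Section 10.4.2.4: subjects who stop drug after an eosinophilic esophagitis (EoE) evaluation are encouraged to continue assessments, but not the Exit challenge.

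The default is set elsewhere. SAP 7.8.1 makes anyone who does not meet the response definition a non-responder. Protocol 9.4.3 counts both dropping out and stopping drug before the Exit challenge as failure.

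**The concern.** Stopping study drug is what changes the meaning of the Exit result; continued visit attendance does not. Protocol 9.4.3 recognises this by treating both events alike, but the estimand section carries over only one of them. The reasons listed for Type C, and largely for Type A, read as reasons for stopping drug, which suggests drug discontinuation may have been what was meant.

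As written, a subject who stops drug, stays on study and is not challenged matches no row of the table, so only the default non-responder rule applies. A subject who stops for the same reason and also leaves can be imputed at the group's response rate. A hypothetical strategy applied to one and not the other does not describe a single well-defined treatment effect. It also means that staying on study, which the protocol encourages, lowers the group's estimate.

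**Working it through.** **Step 1. What an unchallenged subject receives under each analysis.**

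| Analysis, reason type | Leaves the study | Stays on study, off drug |
|---|---|---|
| Primary analysis | non-responder | non-responder |
| (i), any type | non-responder | non-responder |
| (ii), B or C | group response rate | non-responder |
| (ii), A | unclear: text says hypothetical, table has no such rule | non-responder |
| (iii), A or C | non-responder | non-responder |
| (iii), B | group response rate | non-responder |
| (iv), A | non-responder | non-responder |
| (iv), B | group response rate | non-responder |
| (iv), C | not stated | non-responder |

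The two columns clearly differ in three rows: B or C in (ii), and B in (iii) and (iv).

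**Step 2. Inputs.** From SAP 3.2: response 58% high dose, 40% low dose, 4% placebo; 20% dropout; 48 evaluable subjects. 48/(1 − 0.20) = 60 randomized pediatric subjects, as the plan states, which gives 20 per active group and 10 + 10 = 20 in pooled placebo (pooling per SAP 6.6 and 7.8.1). As a check on these inputs, exact enumeration of two-sided Fisher tests with 16 per active group against 16 pooled placebo gives 90.0% power with Holm and 90.9% with Simes, matching the plan's approximate 90%.

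Assumptions not in the documents: the 20% (4 of 20) are the unchallenged subjects in every group; all 4 have Type B or C reasons; the planning rates apply to the 16 who are challenged; and the leave/stay split is the same in each group.

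**Step 3. Analysis (ii), imputing at the rate among challenged subjects.** With m of the 4 leaving the study, the group rate is (16p + m·p)/20.

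- High dose, p = 0.58: m = 4 gives 11.60/20 = 58.0%; m = 2 gives 10.44/20 = 52.2%; m = 0 gives 9.28/20 = 46.4%.
- Low dose, p = 0.40: 40.0% (m = 4) to 32.0% (m = 0).
- Placebo, p = 0.04: 4.0% (m = 4) to 3.2% (m = 0).
- High dose minus placebo: 58.0 − 4.0 = 54.0 points if all leave; 46.4 − 3.2 = 43.2 if all stay. The spread is 10.8 points.
- Low dose minus placebo: 36.0 to 28.8, a spread of 7.2 points.

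**Step 4. Analysis (ii), imputing at the ITT rate with missing counted as failure.** The SAP does not say which group rate is meant. Here the imputed value is 0.464 (high dose) or 0.032 (placebo). With m = 4: high dose (9.28 + 4 × 0.464)/20 = 55.68%; placebo (0.64 + 4 × 0.032)/20 = 3.84%. The difference is 51.8 points, so the range is 43.2 to 51.8.

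**Step 5. Hybrids.** Only Type B subjects count. Each one moves the high-dose rate by 0.58/20 = 2.9 points. If two of the four are Type B the shift is at most 2 × 2.9 = 5.8 points; if none is, it is 0.

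**Step 6. With the event redefined** to cover stopping drug or leaving the study, both columns of Step 1 agree and the leave/stay spread is 0 in every analysis.

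**The case against.** Several stronger readings are tempting, and the documents do not support them.

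- A reader might infer that efficacy results generally depend on visit attendance. They do not. The default rule gives on-study stoppers the same value as treatment policy, so the primary analysis and analysis (i) have a spread of 0. These subjects do have an outcome; what they lack is an assigned strategy.
- A reader might take a taste-related stop as an example for the hybrids. Taste is Type C, which is non-responder in (iii) and has no stated strategy in (iv). The contrast exists for taste only in (ii).
- A reader might assume that updosing failures and EoE stoppers drive the shift. They are closest to Type A, for which the table lists only non-responder. Type B reasons (site closure, camp, school) are arguably those where a subject off drug is least likely to keep attending, and nothing in the documents says how many such subjects to expect.
- A reader might treat the 11.6-point range in the high-dose rate as bias in the treatment effect. It is a one-group upper figure for (ii).
- A reader might conclude that the estimates reflect retention that differs by arm. The documents give no retention data by arm.

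The SAP also has other analyses that touch these subjects. Sensitivity analysis 3 addresses premature drug discontinuation, and the optional worst-case analysis defines missing as no Exit challenge for any reason. Both probe the robustness of the primary result; neither repairs the hypothetical estimand. Finally, the estimand analyses are supplemental and no success claim rests on them.

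These points limit the concern's reach and size. They do not remove the inconsistency in the rows identified in Step 1, where the default rule is itself what makes the stayer differ from the leaver.

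**Conclusion.** The concern holds within limits. Wherever the hypothetical strategy applies (Types B and C in (ii), Type B in (iii) and (iv)), unchallenged subjects with the same reason for stopping are imputed or failed according only to whether they left the study. Under the stated assumptions the high-dose difference from placebo in (ii) can range over 43.2 to 54.0 points, or 43.2 to 51.8 with the ITT rate imputed. These are upper illustrations, since they require all four unchallenged subjects per group to have Type B or C reasons. In (iii) and (iv) the effect is confined to the Type B share, and is smaller unless every such subject is Type B. It is worth correcting because the rule as written gives an inconsistent estimand and the correction is cheap, even though the analyses are supplemental.

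**What to change.** In SAP 7.8.1, text and table:

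1. Define the intercurrent event as permanently stopping study drug or withdrawing from the study, for any reason, with no Exit DBPCFC for any qualifying food. Naming both events closes the gap.
2. Assign Type A, B or C from the treatment-termination reason on the End of Treatment eCRF (SAP 7.1), or from the study-withdrawal reason where that is the event. Put all other reasons in a residual type set to non-responder.
3. Use the observed result whenever an Exit DBPCFC was done.
4. In the same edit, state which group rate is imputed, the rule for Type A in (ii), and the strategy for Type C in (iv).

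The cost is SAP wording before database lock. The reason for stopping is already collected. One small downside: the reasons listed in Protocol 7.2 have no category for taste, camp or school, so sorting Types B and C may need the recorded detail behind the reason, as the current scheme already does. A subject still on drug and on study who is simply not challenged stays under the default non-responder rule; one sentence should say so.

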7.8.2. Secondary Efficacy Endpoints and Analysis

The primary analysis of the secondary endpoints will be performed on pediatric subjects in the ITT Population by treatment group. The analysis will be repeated for the PP Population and relevant subgroups (i.e., subjects who reached 1500 mg of study drug for low-dose group, and subjects who reached 4500 mg of study drug for high-dose group). The analysis will be repeated for all subjects in the ITT Population as well. Descriptive statistics corresponding to the endpoint response rates will be provided for adult subjects. The secondary endpoints will also be analyzed for pediatric subjects in the ITT Population using logistic regression model. The comparison of the secondary endpoints between the pooled ADP101 vs pooled ADP101 will be provided as well.

The secondary endpoints are outlined below:

- Number and percent of subjects who tolerate the 1000-mg level of a single Qualifying Food without dose-limiting symptoms at the Exit DBPCFC (i.e., ≥ 1000 mg desensitization response)
- Number and percent of subjects with ≥ 2 qualifying FAs who tolerate the 600-mg level of each of 2 or more Qualifying Foods without dose-limiting symptoms at the Exit DBPCFC
- Number and percent of subjects with ≥ 2 qualifying FAs who tolerate the 1000-mg level of each of 2 or more Qualifying Foods without dose-limiting symptoms at the Exit DBPCFC

The analyses of the secondary efficacy endpoints will follow the method of the primary efficacy endpoint as described in Section 7.8.1. For these analyses, only the p-values from the Fisher's exact test will be displayed.

The same analyses will be performed on the ITT Population excluding subjects who withdrew from the study prior to completing the Exit DBPCFC for reasons related to COVID-19 (e.g., study site closure).

The last two endpoints will be conducted in the ITT Population, PP Population and relevant subgroups for multi-allergic subjects only.

The plots of each secondary endpoint will be provided for pediatric, adult and all subjects in the ITT population and pediatric subjects in the PP population. The subjects with ≥ 1000 mg desensitization response by reached target dose will be plotted for pediatric subjects in the ITT population.

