9.4.3. Efficacy Analyses

For lists of objectives and endpoints, refer to Section 3.

Since the superiority of ADP101 at different doses over placebo will be tested, the primary and secondary efficacy analyses will be based on the ITT Population. The primary, secondary, and exploratory efficacy analyses will be performed on the ITT Population, as well as the PP Population (based on the ITT principle). Sensitivity analyses, to be described in full in the SAP, will be performed on subsets of the PP Population, e.g., including or excluding subjects who discontinue study drug prematurely due to treatment-related or unrelated reasons. For efficacy analyses, subjects will be analyzed according to randomized treatment.

Primary and secondary efficacy endpoints will be analyzed using Simes' Test with the Holms procedure (multiple p values will be elaborated in the SAP) and Fisher's exact test for dose selection. All individuals failing to achieve the success in the endpoint definition described above in Section 3 will be considered treatment failures. All individuals who drop out of the study or discontinue study drug prior to undergoing the Exit DBPCFC will be considered treatment failures (i.e., Missing = Failure).

Exploratory efficacy endpoints will be analyzed using descriptive statistics. Details will be included in SAP for the study.

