6.6. Data Pooling

In general, data for the 2 placebo treatment groups (low/high dose) will be pooled together, and compared to the low- and high-dose ADP101 treatment groups.

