7.8.1. Primary Efficacy Endpoint and Analysis

The primary endpoint is a ≥ 600 mg desensitization response as determined by tolerating ≥ 600 mg of food protein at the Exit DBPCFC without dose-limiting symptoms for at least 1 qualifying food.

Any subject who does not meet this definition will be considered a non-responder.

Classification as a 1000 mg responder is defined similarly.

Primary Analysis

The primary analysis of the primary endpoint will be performed on pediatric subjects in the ITT Population by treatment group.

The number and percent of subjects with a ≥ 600 mg desensitization response will be reported by treatment group. The primary endpoint hypothesis of superiority of ADP101 over pooled placebo will be tested using the Fisher's exact test. The unadjusted p-values will be reported. The difference in the proportions of responders (ADP101 vs. pooled placebo) with Newcombe 95% CIs will be reported using PROC FREQ procedure in SAS® and the RISKDIFF option.

A sample SAS code for the proc freq is provided below:

Ods output PdiffCL=pdiff

Proc freq

```
data=indata;  
TABLE trtgrp*endpoint/ chisq riskdiff(cl=( newcombe ) correct );  
OUTPUT out=outdata CHISQ RDIF1 ;
```

RUN;

In order to handle the comparison of multiple active groups versus pooled placebo, the overall type-I error will be controlled by the use of the Simes global test (Simes, 1986) with the Holm procedure (Holm, 1979) to adjust for and test the global (joint) hypothesis that at least one of the 2 hypotheses below is rejected.

- H_{01} : proportion of responders in pooled placebo group = proportion of responders in low-dose (1500 mg) group
- H_{02} : proportion of responders in pooled placebo group = proportion of responders in high-dose (4500 mg) group.

The adjustment for multiplicity for the joint hypothesis in support of the primary efficacy endpoint will be performed using the PROC MULTTEST procedure in SAS® (HOLM option). The adjusted p-values will be reported along with the unadjusted p-values described above.

All efficacy-related data will be listed. Tables for the primary efficacy endpoint will include proportion of responders who tolerated at least 600 mg in pooled placebo vs low dose group and pooled placebo vs high dose group in ITT. The unadjusted and adjusted p-values will be displayed.

Sensitivity Analysis

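### SAP 7.8.2 displays no dose-adjusted p-values for the secondary endpoints, although protocol 9.4.3 puts them under Simes/Holm, and SAP Section 9 does not list the change (minor)

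*SAP*

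**What the plan says.** Protocol 9.4.3 (Efficacy Analyses) states: "Primary and secondary efficacy endpoints will be analyzed using Simes' Test with the Holms procedure (multiple p values will be elaborated in the SAP"). Protocol 9.4 adds that the SAP prevails over that section where the two diverge.

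SAP 7.8.1 carries this out for the primary endpoint. Each dose is compared with pooled placebo by Fisher's exact test, and those p-values are called unadjusted. Then: "The adjustment for multiplicity for the joint hypothesis in support of the primary efficacy endpoint will be performed using the PROC MULTTEST procedure" with the HOLM option. On reporting: "The adjusted p-values will be reported along with the unadjusted p-values described above".

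SAP 7.8.2 covers three secondary endpoints: 1000 mg of a single Qualifying Food, 600 mg of each of two or more, and 1000 mg of each of two or more. It says their analyses "will follow the method of the primary efficacy endpoint as described in Section 7.8.1". The next sentence says that "only the p-values from the Fisher's exact test will be displayed". It gives no order of testing, no gatekeeping and no statement that the p-values are nominal.

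SAP Section 9, which lists changes from the protocol's analysis, contains only added exploratory endpoints and analyses.

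**The concern.** The protocol names a multiplicity procedure for the secondary endpoints. The SAP points to the section that contains it and then limits the display to the p-values that precede it. A programmer could run Holm and suppress its output, or never run it. Either way the tables carry no adjusted value, and nothing tells a reader how to take p < 0.05 in them. A secondary result at one dose could then be read as significant when it would not survive the two-dose step named in the protocol. The primary test is not affected.

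**Working it through.** **Inputs.**
- Three secondary endpoints (SAP 4.2 and 7.8.2).
- Two comparisons each, low and high dose against pooled placebo (SAP 6.6 and 7.8.1), so 3 × 2 = 6 tests in the main paediatric ITT analysis. The PP, all-subject, target-dose and COVID-exclusion repeats are not counted.
- Two-sided level of 0.05 (SAP 6.1).
- Paediatric group sizes of 20, 20 and 10 + 10 (SAP Table 1).
- Planning values of 16 completers per active dose and 16 on placebo, with response rates of 4%, 40% and 58% (SAP 3.2).

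**Step 1: the plan's own figure.** Exact enumeration of two-sided Fisher tests at 16/16/16 with a shared placebo group was used. Rejecting when the smaller p ≤ 0.025 (Holm's first step) gives power of 89.99%. Rejecting also when both p ≤ 0.05 (Simes) gives 90.9%. The stated power of about 90% is reproduced, so the two-dose step with pooled placebo is taken as the plan's working procedure. The documents give no power or error figure for the secondary endpoints.

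**Step 2: what the adjustment changes.** With equal groups of 20 and no placebo responders, the two-sided Fisher p-value is 2 × C(20,k)/C(40,k).
- k = 5: 2 × 15,504/658,008 = 0.047.
- k = 6: 2 × 38,760/3,838,380 = 0.020.

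For two doses, Holm doubles the smaller p-value. The larger adjusted value is the maximum of that and the larger raw p-value.
- 5/20 at one dose and 4/20 (p = 0.106) at the other, placebo 0/20: the smaller adjusted p is 2 × 0.0471 = 0.094. The raw table shows a result below 0.05; the adjusted one does not.
- 5/20 and 6/20: adjusted values are 2 × 0.0202 = 0.040 and max(0.040, 0.047) = 0.047. Both still pass.

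The two multi-food endpoints use only multi-allergic subjects, so their groups are smaller than 20.

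**Step 3: error within one endpoint.** Exact chance of at least one false positive over the two doses when all three groups share the same response rate:

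| Common response rate | 20 per group, raw | 20 per group, Holm | 12 per group, raw | 12 per group, Holm |
|---|---|---|---|---|
| 4% | 0.15% | 0.02% | 0.01% | 0.00% |
| 10% | 2.2% | 0.6% | 0.5% | 0.1% |
| 20% | 4.2% | 1.8% | 2.3% | 0.6% |
| 30% | 4.6% | 2.1% | 3.2% | 1.0% |
| 50% | 3.8% | 2.6% | 4.3% | 1.3% |

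Twelve per group is 60% of 20, an assumed multi-allergic share. At the rates checked, Fisher's conservatism keeps even the raw two-dose error below 5%.

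**Step 4: error over all six tests.** This was simulated under a global null with 20 per group, correlated foods and 3,000 to 4,000 runs per scenario. The share of multi-allergic subjects, the number of foods and the correlations are assumptions, not figures from the documents.

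| Null response per food at 600 mg | Raw, two foods if multi-allergic (60% of subjects) | Raw, two to five foods (60–90% of subjects) | Holm within each endpoint, both settings |
|---|---|---|---|
| 4% | 0.1–0.4% | 0.2% | 0.03% (two to five foods) |
| 20% | 4.6–5.4% | 8.8% | 1.7–3.8% |
| 40% | 9.1–10.2% | 11.8–12.7% | 4.3–6.9% |
| 60% | 11.9–12.6% | not run | 6.5–6.7% |

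Holm within each endpoint can still exceed 5% over the six tests, because it does not act across the three endpoints.

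**The case against.** The protocol itself hands the detail to the SAP and lets the SAP prevail, so the SAP was free to choose. That stands: the change is undeclared, not unauthorised. The rule on precedence settles which text governs but does not disclose the departure.

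The reference to Section 7.8.1 may import Holm, leaving only the display restricted. Since Holm for two doses can be worked out by hand from the two raw p-values, no information is lost. This also stands, and it is a main reason the point is minor. It does not resolve the ambiguity, because on either reading the adjusted value is not reported. The table shells are a separate document and may label the p-values nominal; that cannot be seen from here.

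A reader might infer that the secondary endpoints will be claimed as confirmatory. The documents do not say so. The rule on claiming significance (protocol 9.1, SAP 3.2) concerns the primary endpoint only.

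A reader might also infer that control over all six tests was promised and then withdrawn. It was not: protocol 9.4.3 gives no hierarchy or family across the three secondary endpoints. What is missing from the display is, at most, the two-dose adjustment within each endpoint.

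**Conclusion.** The divergence is real and minor. Under the governing text no dose-adjusted p-value is shown for any secondary endpoint, and SAP Section 9 is silent. The practical consequence is limited to borderline single-dose results such as 5/20 against 0/20.

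The six-test error is well under 1% at 4% response per food. The documents' 4% is a subject-level placebo rate for the primary endpoint, and it is the only planning placebo rate they give. The error is about 5% at 20% with two foods per multi-allergic subject, and 8.8% with two to five. It reaches about 9% to 13% only at 40% to 60%. Such rates would require about half of untreated challenges to be tolerated at 600 mg, for foods that elicited symptoms at or below 100 mg at Screening. Nothing in the documents supports that.

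It is tempting to quote 1 − 0.95^6 = 26.5%. That is neither the error rate nor an upper bound here. It assumes six independent tests each at exactly 5%, whereas both doses share one placebo group, the endpoints are nested, and Fisher's test runs well below 5% at these sizes. It should not be used.

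**What to change.** In SAP 7.8.2, replace the display sentence with wording to this effect:

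> For each secondary endpoint, the PROC MULTTEST HOLM step of Section 7.8.1 will be applied to the two dose comparisons with pooled placebo. Unadjusted and adjusted p-values will both be displayed. This controls error across the doses within an endpoint, not across the three endpoints.

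If the sponsor prefers unadjusted p-values, label them nominal in SAP 7.8.2 and in the tables, and list the departure from protocol 9.4.3 in SAP Section 9. Testing the three endpoints in a fixed order after the primary is an optional addition; neither document promises it.

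The cost is one existing procedure call per endpoint and one column per table, made before database lock. The downside is that secondary p-values become slightly less favourable.
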